#### 7.12 Social Harms Reporting

Although study sites make every effort to protect participant privacy and confidentiality, it is possible that participants' involvement in the study could become known to others, and that social harms may result (i.e., because participants could become known as HIV-infected or at "high risk" for HIV infection or participants could potentially disclose their sexual orientation). For example, participants could be treated unfairly or discriminated against, or could have problems being accepted by their families and/or communities and/or employer.

Social harms that are judged by the study site investigator to be serious or unexpected will be reported to responsible site IRB at least annually or according to their individual requirements. In the event that a participant reports social harm, every effort will be made by study staff to provide appropriate care and counseling to the participant, and/or referral to appropriate resources for the safety of the participant as needed.

#### 7.13 Monitoring untoward effects associated with or resulting from study

Site staff must first follow their own IRB's procedure for reporting and managing untoward effects.

There are three types of untoward effects to be identified: (1) those related to the participant, (2) those related to the study staff and (3) those related to the neighborhood or community where the study is being implemented.

First, the study will catalogue any untoward effect related to the participant. Reporting is required for occurrences including social harms, psychological distress and serious life threatening events such as suicide attempts. These may be immediately apparent to the study staff, such as the participant's emotional upset requiring referral for counseling; or they may be delayed and reported later to study staff, such as physical harm to an individual for having participated in the study. Study staff will notify the team of these untoward effects using the iTech QNS accessible through the iTech website (https://itechnetwork.org). Study staff will be briefed during the training on the scope of possible untoward effects and instructed to report events.

Second, study staff may encounter untoward events during sessions that personally affect them. Training and guidance will seek to minimize this risk. Nonetheless, an assessment of the cost of conducting this study must include cataloguing these events as well. The protocol chairs should be notified of these events so that they may be immediately addressed, evaluated, and guidance modified or expanded to minimize similar risk to other staff.

All untoward events related to the participant or study staff will be graded for severity by site study staff according to the definitions outlined in Table 10-1 (Appendix VI), as per ATN procedures. Reporting of all UEs graded 3 or higher will be expedited. Please see Data Safety and Management Plan for additional details.

# 8. DATA COLLECTION AND SITE MONITORING

# 8.1 Development of Protocol and Case Report Forms

The Protocol Team, in collaboration with the ATN iTech Management Core and the iTech Analytic Core, is responsible for the development of this protocol as well as the Case Report Forms (CRFs) needed to collect the information required to implement this protocol.

# 8.2 Data Records

Participant-related study information will be identified through a study ID number (SID) and participant code on all participant CRFs, audio files, transcripts, and Computer Assisted Self Interviewing (CASI) files. Participant code consists of the participant's first initial and two-digit date of birth. Participant names or other personal identifying information will not be used on any study documents and will be redacted from any qualitative transcripts. Participants enrolled in the Phase I will also receive a Trial ID number (TID) to identify their assigned PK sampling schedule. Participant names and their SID/TID will be stored separately from other study information, accessible only to designated study staff, iTech site monitors, and representatives from the NICHD. Original source documents for individual participants will be accessible only to the study staff. Data from original source documents will be transcribed on CRFs as applicable.

## 8.3 Research Staff Training

All proposed study staff have participated in the required trainings in participation and conduct of studies that involve human subjects, and any future study staff will do so upon hiring. Training for all research staff includes (but is not limited to) an overview of the study, study procedures and human subjects issues (informed consent process, confidentiality), a demonstration of all technology components, methods for establishing comfort with the sensitive issues, including discussion of sexual behaviors, that will likely arise in the course of the assessments, review of the study instruments, their required elements and the inherent flexibility built into them, Human Subjects Protection, Good Clinical Practice, Child Abuse History Clearance, FBI Criminal History Background Check, informed consent, quality management, confidentiality, and reporting of adverse events.

## 8.4 Data Collection

#### 8.4.1 CRFs

Study monitoring data, including information about eligibility, demographic data and monitoring untoward effects, will be collected on CRFs. All CRFs for this study will be available for download from the iTech Box account, a secure content management platform.

## 8.4.2 Web-Survey Data

Data collected using a web-based computer-assisted survey method will be on a portable computer, tablet, or mobile phone via an internet-based application. All survey data will be collected using SurveyGizmo. Data

will remain confidential; no personal identifying information will be collected during the computer session. The participant's unique study ID will be used in order to link the interview responses to the participant's CRF data. We use SSL encryption for transfers of information online and data will be stored in the secure, HIPAA-compliant servers of Qualtrics. The Emory team maintains a business partner HIPAA agreement with SurveyGizmo.

#### 8.4.2.1 Data Security

To ensure data privacy, as soon as data is entered (in real-time), it will be encrypted during transmission using Secure Socket Layer (SSL) technology. The data will then be immediately stored in a secure database on an server within the Emory data center.

We clean, manage, and download the survey data directly from the SurveyGizmo application interface. The survey data collected through SurveyGizmo is encrypted while in transfer using SSL certificates, encrypted at the disk level in the database servers, and encrypted at the row level. Access to the SurveyGizmo account where the data can be downloaded is password-protected with a dual authentication password. The data collected through our web application is encrypted while in transfer using SSL certificates and access to the administrative web application where the data can be downloaded is password-protected with a collected using sufficiently complex passwords for each approved user.

#### 8.4.3 BlueJeans Platform Description

For the in-depth interviews that occur over video chat, the BlueJeans platform – or a comparably secure videoconferencing platform - will be used. BlueJeans is compatible with PCs, Macs, and any device with a web browser, including tablets and smartphones. Unlike other video-chat platforms (e.g. Skype), BlueJeans is HIPAA-compliant. BlueJeans includes the following functions to protect users:

*Media handling and encryption.* In WebEx, Vidyo, Tandberg, and Polycom architectures, media is sent to a server (also called a video relay or MCU). Although encryption is applied from the user's computer to these servers, the servers still have full access to the user's media. In contrast, Blue Jeans does not record or store your information; they simply encrypt and transmit it. Blue Jeans Network does not store any video conference content, in any format. This security infrastructure means Blue Jeans has no control over the content shared via video conference. BlueJeans supports standards-based encryption (AES-128) for video conferencing.

*Infrastructure and network security*. BlueJeans employs a wide range of security management. This includes network firewalls throughout the infrastructure to create security zones for different applications and services. BlueJeans also deploys proxy servers that terminate all third party/customer traffic at a proxy layer. All web traffic passes through industry-leading load balancers to protect against a suite of application attack vectors. Beyond the firewall, proxy servers, and load balancers, BlueJeans also periodically scans for network, port, and application-level vulnerabilities. Vulnerability scans are conducted by a leading third-party SaaS provider, in addition to some special-purpose, in-house scanning tools. Furthermore, all of the third-party applications and operating system software is checked for security advisories and is patched periodically. Routers, firewalls, load balancers, and proxy application servers are all configured to mitigate numerous types of DOS attacks. BlueJeans also engages with third party consultants to perform penetration testing of the service.

*No-install client.* Video conferencing software clients tend to be large and to leave a big footprint on the user's system. Almost all of them require administrator permissions to install. Once the client software gains administrator permissions, they can severely compromise computer security. BlueJeans offers a browser-based conferencing system that does not require administrator permissions or installation.

BlueJeans offers the HIPAA-required Business Associate Agreement (BAA) where BlueJeans agrees to be responsible for keeping all patient information secure and to immediately report any breach of personal health information. In this study, University of Pennsylvania will maintain a BAA with BlueJeans, and this will be extended to cover the proposed activities. The BlueJeans sessions will include identifying information (e.g., images of the participant, voice recordings). All identifying information will be stripped from the data transcripts before they are sent to the analysis team for content analysis.

#### 8.4 Data Submission

#### 8.4.1 CRFs

During study conduct, the SRVs will maintain the CRFs in secured locations, and transmit CRF data to the AC either electronically using DFexplore or by submitting scanned paper forms using DFSend. DFexplore and its DFdiscover platform is a leading multi-site database environment for HIV RCT that can receive and transcribe CRF data via scanned PDFs, or allow for direct electronic data entry. It provides for monitoring form completion and data quality, and a system for data querying and resolution with SRVs, while maintaining an audit trail. The AC uses DFexplore for MSM studies and RCTs and data is maintained by the parent company DF/net on a cloud-based server with Microsoft Azure.

#### 8.4.2 Audio Data

In-depth interviews will be audio-recorded to allow for verbatim transcription of the interview and checked for accuracy and completion. We will format all transcripts and import them into qualitative data analysis software, Dedoose. Data analysis will be primarily conducted by [name] and other DREAM study team members at the University of Pennsylvania when appropriate. One year after study completion, audio recordings will be destroyed.

#### 8.4.3 Survey Data Transmission

Only authorized users will be able to access and open the survey through SurveyGizmo. To ensure data privacy, as soon as data is entered (in real-time), it will be encrypted during transmission using Secure Socket Layer (SSL) technology. The data will routinely be downloaded and stored in a secure database on an Emory server within the AC data center.

### 8.4.4 Retention data

N/A

#### 8.5 Data Quality Assurance

Investigators receiving federal funding must adhere to the Code of Federal Regulations (CFR) to protect research participants and produce reliable study information. Sites participating in research sponsored by the

NICHD need to have an internal quality assurance (QA) plan that will identify problems and correct errors in research study records.

Behavioral data will be collected via Qualtrics. Qualtrics is a HIPAA-compliant, web-based electronic data collection tool that ensures data quality through the standardization of data collection procedures. The PIs and study staff will be responsible for data monitoring and quality assurance. There will be ongoing communication within study team to monitor data collection, participant safety, and compliance with the study protocol.

### 8.6 Role of Data Management

The iTech AC will provide instructions concerning the recording of study data on the CRFs and entry of the data into the AC data management systems. Behavioral components of the application (e.g., recruitment, video interviews, transcription and analysis) will be overseen by the UPENN team. Clinical components of the application will be overseen by the JHU team. The iTECH AC will also offer data monitoring support for the online screeners, data management, and statistical support for trial analyses.

### 8.7 Study Site Monitoring and Record Availability

Site monitors from the MC and AC may visit participating study sites to review a selected portion of the individual participant records, including assent/consent forms, CRFs and supporting source documentation to ensure the protection of study subjects, compliance with the protocol, and accuracy and completeness of records. Regulatory files, as required, will also be inspected to ensure that regulatory requirements are being followed.

The site investigator will make study documents (e.g., consent forms, case report forms) *and pertinent hospital or clinic records* readily available for inspection by the local IRB, the site monitors, the NICHD, the Office of Human Research Protection (OHRP), or the sponsor's designee for confirmation of the study data.

## 9. STATISTICAL CONSIDERATIONS

#### 9.1 Overview and Summary of Design

This is an exploratory, open label study to compare the safety, PK, PD, and acceptability of the formulation of a TFV microbicide enema. The goal of the study is to describe the pharmacokinetic parameters in a population of a TFV douche currently under development in a population of young men who have sex with men (YMSM).

Eligible YMSM will be contacted by site staff to schedule an in-person Screening Visit at the ATN site. A Screening Visit will take place up to 45 days prior to the Baseline enrollment Visit. At this visit, YMSM ( $n\approx48$ ) will learn about the Phase I trial and be invited to participate in the study. All participants will be consented and those who agree to participate in the Phase 1 portion the study will complete Screening Procedures, which includes a medical exam, HIV/STI testing, and a brief, online survey regarding their sexual behaviors, prior experiences and comfort using rectal products, experiences and willingness to participate in the trial and scheduled for their PK/PD visit once all HIV/STI labs have been confirmed. YMSM who choose not to participate in the Phase I trial or who are ineligible to participate due to labs results ( $n\approx32$ ) will be invited to participate in an online-facilitated in-depth interview (IDI). The screening, enrollment, dosing, and termination visits will take place at Johns Hopkins University.

After completing the screening evaluation, we will enroll 16 evaluable participants. YMSM who are willing and cleared to participate in the Trial visit will be asked to use a single dose of a tenofovir (TFV) rectal microbicide douche (600mg TFV in 125mL 0.45% NaCl [half-normal saline]) at the Hopkins study site. Prior to using the TFV douche, baseline samples (see Appendix 1) will be collected to establish pre-dose conditions for safety assessments.

YMSM will then receive a single dose of TFV douche at the research unit, and, asked to retain the douche without defecation for 5 minutes, if possible. Subsequently, participants will be instructed on how to expel the douche contents. The amount of time that the douche was retained and the volume of expelled effluent will be measured. Post-dose observations and data collection will follow at 1, 6, 24, and 72 hours, using a sparse PK sampling design in which plasma and peripheral blood mononuclear cells (PBMC) are collected at each designated time. Participants are randomized to only one time point for flexible sigmoidoscopy with rectal biopsies at either 1, 6, 24, or 72 hours after dosing (thus, providing 4 subjects at each time point). Anoscopy, with rectal fluid collection will occur pre-dose, 1, 6, 24 or 72 hours after dosing to coincide with the time of each participant's flexible sigmoidoscopy. Microbiome specimens will be collected via anoscopy pre-dose and at 24 hrs post-dose.

Between sampling windows, YMSM will complete a web-survey examining their perceived reactions and comfort using the study douche, factors influencing product use in the future, and comfort with the trial procedures. The survey will be administered after dosing but scheduled not to interfere with other study assessments. Sampling for safety, PK, PD, and acceptability assessments will be collected according to the schedule of events. Phase I Trial participants will complete in an IDI as part of their termination visit.

### 9.2 Study Endpoints

Study endpoints to be assessed are each paired with specific objectives as listed in Section 3 Objectives & Endpoints.

### 9.3 Study Hypotheses

This protocol and derived data will provide information that will address, even if not completely answer, the following study hypotheses:

- YMSM will find the product to be acceptable and behaviorally congruent with their rectal hygiene practices
- The TFV douche will be safe and acceptable when applied rectally
- The TFV douche will exceed target colon MMC concentrations for a period of 1 hour to 72 hours postdose
- Concentrations in various compartments after enema will provide an important parallel to concentrations seen after TFV gel (historic control from previous study) and will provide correlating data to a prior study carried out in adult MSM.

### 9.4 Accrual and Sample Size

We expect to screen 48 YMSM willing to participate in the in-person Screening Visit. We derive this estimate based on prior experiences in rectal microbicide trials through the Microbicide Trials Network (MTN). We will need to screen and consent approximately 48 YMSM in-person. Assuming a 1:3 ratio of willingness to enroll in a biomedical clinical trial, we will enroll 16 YMSM (n=8 between the ages of 15-19; n=8 between the ages of 20-24) for the Phase I Safety Trial.

A sample of 16 YMSM enrolled in the DREAM ATN trial will allow for maximal comparability with DREAM-01, which included the same product in 18 adults. Comparing 8 participants of DREAM ATN to counterparts in each arm of DREAM-01 provides 80% power, with 2-sided type I error of 5% to detect a difference of 1.0 standard deviations.

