DREAM-01 compared three different douche formulations including iso-osmolar Product A (220 mg TFV in 125 mL normal saline [0.9% NaCl]), iso-osmolar Product B (660 mg TFV in 125 mL normal saline), and Product C (660 mg TFV in 125 mL half-normal saline [0.45% NaCl], a hypo-osmolar formulation. Each participant received each of the 3 formulations to allow paired comparisons for safety and PK. We enrolled 18 healthy HIV-uninfected adult MSM, to identify the dose and osmolarity that achieves target colonic tissue cell TFV-DP concentrations to exceed iPrEX tissue EC90, based on levels from 4 PO TDF doses/ week. Semi-intensive sampling of plasma and PBMCs and sparse sampling of rectal fluid and colon tissue was performed. Ex vivo explant susceptibility to HIV infection was assessed via colon biopsies, and acceptability was assessed via questionnaires and in-depth interviews. A within-subject comparison of safety, PK, PD, distribution, & acceptability of 3 TFV douche formulations was conducted. 

The douche was demonstrated to be safe and well tolerated, with high acceptability to participants. All three products were generally well-tolerated. There were three Grade 3 Adverse Events (AE), one in each study phase, none of them deemed to be product related. There were a total of two AE's that were deemed product-related (rectal dryness and blood-tinged enema effluent, in a participant with history of internal hemorrhoids), and both were Grade 1 (See Table 4). Adverse events were also not dose related.

	While on Study	During Baseline	During Phase 1	During Phase 2	During Phase 3
		No Study Product	Study Product A	Study Product B	Study Product C
		(Visit 2)	(Visits 3-7)	(Visit 8-11)	(Visit 12-16)
Participants who expe	rienced an AE [3]	·		·	·
Grade 1	29	0	13	8	8
Grade 2	14	1	8	2	3
Grade 3	3	0	1	1	1
Grade 4	0	0	0	0	0
Grade 5	0	0	0	0	0
Total	46	1	22	11	12
Total # of AEs reported	d [8]		1		
Grade 1	60	0	29	10	21
Grade 2	20	1	10	2	7
Grade 3	3	0	1	1	1
Grade 4	0	0	0	0	0
Grade 5	0	0	0	0	0
Total	83	1	40	13	29

Table 4. Aggregate adverse events and	histology results from DREAM-01 (n=18)	

*Histology*. Rectal biopsies from baseline (pre-dose) and post-dose at times associated with PK and PD sampling (1, 3, 6, 24, 72, and 162 hours) and displayed in Table 5. AE refers to a scale established for evaluation of inflammatory bowel disease.

[figure not shown]

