#### 9.6 Data Analysis

For primary endpoints, sensitivity analyses will be performed by age group (15 to 19-year-old YMSM; 20 to 24-year-old YMSM). PK estimates will be reported overall and per group, given need to examine whether there are significantly different TFV-DP rectal tissue levels across these two age groups. Safety data will be reported in the aggregate for the overall population, as safety is not expected to differ significantly by age group. As noted above, sample size is conditioned to a great degree on having a comparable, complete, and relevant cohort for comparison to DREAM-01. Descriptive statistics and graphics will be used to summarize the characteristics of endpoints across each step of the study. Continuous measures will be summarized by

means and standard deviations or median and interquartile range depending on data distribution. For binomial endpoints, 95% exact confidence intervals will be calculated. Given the small sample size and possible non-normality of the data, non-parametric tests will be used to test for differences among (Kruskal-Wallis) and between (Wilcoxon rank sum test) test formulations.

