Pharmacokinetics: To characterize the systemic and compartmental pharmacokinetics of a TFV douche following rectal application, as measured by TFV concentrations in plasma, rectal fluid and rectal mucosal tissue homogenates and cells. Pharmacokinetic parameters will be compared to data from studies using rectal dosing of TFV in DREAM-01 and other oral TFV dosing studies in adults, which also included colorectal biopsies. Pharmacokinetics in blood plasma and PBMCs, colon tissue homogenate and cells, and rectal fluid for the TFV-based douche will be evaluated after rectal administration. The primary analysis will use noncompartmental methods to estimate pharmacokinetic parameters, including peak concentration (Cmax, time to peak concentration ( $T_{max}$ ), area under the matrix concentration-time curve from 0 to infinity ( $0 \rightarrow \infty$ ), and terminal elimination half-life. For sparsely sampled matrices (colon tissue homogenate, colon tissue cells, and rectal fluid), we will use population PK methods to build PK models describing individual PK parameter estimates and typical values for the population along with significant covariates (possibly weight, age, pharmacogenetics, creatinine clearance). Tenfovir and TFV-DP assays will be performed by the Clinical Pharmacology Analytical Laboratory (CPAL) at Hopkins and are validated following FDA bioanalytical guidance and approved by an NIH-cross network Clinical Pharmacology Quality Assurance (CPQA) program before used in clinical studies. Primary PK analyses will be testing for (1) differences in PK measures between the two age groups (Kruskal-Wallis) and (2) comparison with DREAM-01 PK results.

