#### 9.7 Missing Data

All reasonable efforts will be made to obtain complete data for all participants; however, missing observations will occur due to missed visits, participants lost to follow-up, or noncompliance. Research participants who fail to complete dosing and evaluations relevant to all study product doses for any reason may be replaced at discretion of the study site investigator after consultation with the Sponsor. Data for PK and distribution will be required of all periods of the study or the research participant will be replaced.

Several procedures will be used to conduct data analysis when data for either outcomes or covariates are missing. The first step will be to assess the extent and pattern of missing data. If data are missing for only a few cases, then data analysis will be conducted only on study participants with complete data. However, when such a strategy would result in loss of data from a substantial proportion of participants, or if this approach would lead to biased or inaccurate results, then some form of imputation will be performed. The form of imputation used will depend on the nature of the data that are missing. For example, data that are collected repeatedly might be imputed using the "last value carried forward" method; and in some instances, interpolation between neighboring points might also be used. When the primary endpoint is missing, one data analysis will be conducted using only cases with the endpoint. Subsequent analysis will be done where missing endpoints are imputed. Hot-deck imputation or regression imputation may also be used in this context.

As previously noted, all available data will be used for safety purposes. All available data will also be used for descriptive purposes. Formal statistical comparisons between study products, however, must necessarily be limited to subjects who complete use of study products. The between-product comparisons are critical to allow the use of the data in this study to guide future rectal microbicide development. Accordingly, the protocol principal investigators in consultation with the site investigators will determine if research participants who fail to complete all PK collection sessions should be replaced. Replacement subjects would be assigned the same sampling schedule as the subject they are replacing.

The familywise error rate corrections will be used to adjust for multiple comparisons.

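### The 80% power in section 9.4 does not reproduce: 8 participants against at most 18 DREAM-01 adults gives about 62% for a 1.0 SD difference

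*Combined protocol and SAP*

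**What the plan says.** Section 9.4 plans 16 participants, 8 aged 15–19 and 8 aged 20–24, and justifies this by comparability with DREAM-01. Its power statement is: "Comparing 8 participants of DREAM ATN to counterparts in each arm of DREAM-01 provides 80% power", with a two-sided type I error of 5% and a difference of 1.0 SD. It names no test and gives no size for the DREAM-01 arm.

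The comparator size is stated elsewhere. Section 9.4 itself says DREAM-01 gave the same product to 18 adults, and section 1.6 confirms "We enrolled 18 healthy HIV-uninfected adult MSM" and "Each participant received each of the 3 formulations to allow paired comparisons for safety and PK".

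Section 9.6 (Pharmacokinetics) defines the primary PK analyses as "testing for (1) differences in PK measures between the two age groups (Kruskal-Wallis) and (2) comparison with DREAM-01 PK results". The general part of section 9.6 says "non-parametric tests will be used to test for differences among (Kruskal-Wallis) and between (Wilcoxon rank sum test) test formulations". Section 9.7 ends with "The familywise error rate corrections will be used to adjust for multiple comparisons", without a method or a list of the tests covered.

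**The concern.** The plan supplies every input for the power calculation except the test, and those inputs do not lead to 80%. Eight against 18 independent people is a small, unbalanced comparison, and 1.0 SD is not a large enough difference for it.

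The study is exploratory, but this sentence is the plan's only power figure for a primary PK comparison. Sections 1.6 and 1.7 state the aim of showing that PK in young MSM agrees with PK in adults, as a bridge for later development. If readers believe that 8 participants give 80% power, they may take a non-significant difference as support for agreement. At the true power, a full 1.0 SD difference would be missed about 4 times in 10.

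**Working it through.** **Inputs.** n₁ = 8, difference d = 1.0 SD, two-sided α = 5%, stated power 80% (section 9.4). n₂ ≤ 18 (sections 9.4 and 1.6). DREAM-01 was a crossover, so its three arms are the same 18 people. They are different people from the DREAM ATN participants, so the groups are independent.

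**Method.** Two-sample t-test with pooled variance. The non-centrality is δ = d / √(1/n₁ + 1/n₂), with n₁ + n₂ − 2 degrees of freedom. Power is the probability that a non-central t variable with parameter δ falls outside ± the critical value.

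**The plan's comparison, 8 v 18.**
- 1/8 + 1/18 = 0.1806; the square root is 0.4249; δ = 1/0.4249 = 2.353.
- Degrees of freedom 24, critical value 2.064.
- Power = **61.7%**. The normal approximation, Φ(2.353 − 1.960), gives 65.3%.
- The difference detectable with 80% power is **1.24 SD**.

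**Can any reading give 80%?** Power at 1.0 SD, two-sided 5%:

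| Comparison | δ | Power |
|---|---|---|
| 8 v 16 (if only 16 adults were usable; assumption) | 2.309 | 59.8% |
| 8 v 18 | 2.353 | 61.7% |
| 8 v 54 (every DREAM-01 dose counted as a separate adult) | 2.640 | 73.8% |
| 8 v 400 | 2.801 | 79.8% |
| One-sample t, n = 8 | 2.828 | 68.1% |
| One-sample normal formula, n = 8 | 2.828 | 80.7% |
| 16 v 18 | 2.910 | 80.6% |

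Only two readings that use the trial's own numbers reach 80%. One uses all 16 participants, which is not what the sentence says. The other is Φ(√8 − 1.960) = Φ(0.868) = 80.7%, which ignores the sampling error of the DREAM-01 mean and uses a normal instead of a t critical value. The required n from that formula is (1.960 + 0.842)² = 7.85, which rounds up to 8. This may be where the figure came from, but the plan does not say.

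**Rank test.** Section 9.6 names the Wilcoxon test for comparing formulations, and no test for the DREAM-01 comparison. If Wilcoxon were used, simulation with normal data gives about 58% for 8 v 18 and about 78% for 16 v 18.

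**The other primary PK comparison, age group v age group (8 v 8).** δ = 1/√(1/8 + 1/8) = 2.0, 14 degrees of freedom, critical value 2.145: power 46.1% (about 44% by rank test), with 80% power at 1.51 SD. Section 9.4 makes no claim for this comparison; the figure is given for context.

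**Effect of multiplicity.** Section 9.7 names no procedure. If 5% were split equally over the two primary PK comparisons (an assumption), each would be tested at 2.5%, and t-test power would be 49.6% for 8 v 18, 71.0% for 16 v 18 and 33.8% for 8 v 8.

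**Scope.** All these figures assume one value per participant. Colon tissue cell TFV-DP, the primary PK endpoint (section 2.2), is biopsied at one post-dose time per participant, "thus, providing 4 subjects at each time point". Section 1.7 excludes participants under 18 from biopsy. The figures therefore do not apply to it.

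**The case against.** The arithmetic for 8 v 18 is not in dispute; the objections concern weight and scope.

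- *The study is exploratory, and its size was chosen for comparability with DREAM-01 rather than for power.* True, and a small exploratory study is acceptable. A stated power must still follow from its inputs, and section 9.6 calls this comparison primary.
- *The 8 may not be one age group.* Section 9.4 does not say so explicitly. It is the natural reading of 8 + 8, and the result for 8 v 18 is the same whichever 8 are meant.
- *Counterparts could mean matched pairs.* No matching is described, and a paired t-test on 8 pairs, with 1.0 SD taken as the SD of the differences, gives 68.1%.
- *The familywise sentence sits at the end of the missing-data section, and the acceptability paragraph of section 9.6 says there will be no adjustment.* It is unclear which tests section 9.7 governs. The 2.5% figures are therefore conditional, but the shortfall at unadjusted 5% does not depend on them.
- *The corrected figures do not cover the primary PK endpoint.* This stands. Population PK modelling might yield individual tissue estimates, but section 1.7 doubts that the sample is large enough for robust ones. The corrected text should state the limit rather than leave the reader to assume that the power covers tissue.

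**Conclusion.** The stated 80% is wrong for the comparison described. With 8 participants against the most favourable arm size of 18, power at 1.0 SD and two-sided 5% is 61.7% by t-test, about 18 percentage points lower, and 80% needs about 1.24 SD. This rests on independent groups, equal variances, normal data and all 18 adults having usable Product C data; fewer adults would lower it. A rank test (about 58%) or a multiplicity correction (49.6% under an equal two-way split) would also lower it. The full-sample comparison, 16 v 18, does give about 81% by t-test at unadjusted 5%. The error should be corrected, but it does not call for a change of design.

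A secondary point: section 9.6 says "Pharmacokinetic parameters will be compared to data from studies using rectal dosing of TFV in DREAM-01" and describes how PK parameters will be estimated, but gives no test, estimand or margin for the comparison itself.

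**What to change.** Replace the power sentence in section 9.4 with text to this effect:

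> For measures with one value per participant, at unadjusted two-sided 5% and assuming usable Product C data from all 18 DREAM-01 adults, all 16 participants v DREAM-01 gives about 81% power for a 1.0 SD difference (t-test; about 78% if Wilcoxon). One age group v DREAM-01 (8 v 18) gives about 62% (58% if Wilcoxon), with 80% power at 1.24 SD. The two age groups (8 v 8) give about 46% (44% by rank test). Fewer usable adults or the correction in section 9.7 would lower these figures; if 5% were split equally over the two primary PK comparisons, they would be about 71%, 50% and 34% (t-test). They do not apply to colon tissue TFV-DP, which has at most 4 participants per post-dose time and none under 18.

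Optionally, section 9.6 could name the test or estimand for the DREAM-01 comparison, or call it descriptive, and say that a non-significant difference at these sizes is not evidence of PK congruence.

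The cost is one replaced passage and perhaps two added sentences. No participants, procedures or data are added; the stated power becomes less favourable.
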